6.6.5 Study Drug Assignment Questionnaire

After study procedures at Visit 3, the subject will be asked to guess what their first treatment was, and what their second treatment was from the choices of “Xeris Glucagon, G-Pen, administered by auto-injector”, and “Comparator Glucagon, GlucaGen Hypokit, administered by needle and syringe”.

This data will be analyzed descriptively with counts and percentages by treatment. Percentage of guessing will be compared against 50% using binomial proportion for each treatment.

This will be conducted based on the PP population only.

6.7 Subgroup Analysis

Analysis of subgroups will not be performed in this study.

6.8 Interim Analysis

Interim analysis will not be performed in this study.

7 DATA HANDLING CONVENTIONS

7.1 Missing Data

Unless specified in any of the previous sections, no other missing data will be imputed.

7.2 Repeated and Unscheduled Visits

Unless specified in any of the previous sections, the principle of ‘last observation priority’ will be used to handle the situation of a repeated visit. Worst post-baseline assessments will be defined using all visits, including unscheduled.

7.3 Conversion of Plasma Glucose Values

For measurements of plasma glucose standard units will be considered as mg/dL. All measurements in mmol/L will be converted into mg/dL with next rule applied:

$$1 \text{ mmol/L} = 18.0182 \text{ mg/dL}$$

8 PLANNED LISTINGS, TABLES AND FIGURES

Please see the Appendix 1.

Note: this is the planned Table of Contents. Based on the actual data, table numbers, table names and structures may change.

9 SOFTWARE REQUIREMENTS

SAS – Version 9.4 or higher.

WinNonlin - Professional Version 5.2 or higher.

Excel - Microsoft Excel 2007 or higher.

10 DEVIATIONS FROM PLANNED ANALYSIS

For timing parameters mixed model analysis was replaced by time-to-event analysis.

APPENDIX 1: LIST OF TABLES, LISTINGS AND FIGURES

Tables	
Number	Title
14.1.1.1	Summary of Patient Disposition (All Enrolled Patients)
14.1.1.2	Summary of Patient Disposition by Treatment (Intent-to-Treat Population)
14.1.1.3	Summary of Analysis Populations (All Randomized Patients)
14.1.2	Summary of Demographic and Baseline Characteristics (Intent-to-Treat Population)
14.1.3.1.1	Summary of Vital Signs – Blood Pressure and Heart Rate by Treatment (Safety Population)
14.1.3.1.2	Summary of Vital Signs – Blood Pressure and Heart Rate by Treatment Sequence (Safety Population)
14.1.3.2.1	Summary of Vital Signs – Weight, Respiratory Rate and Temperature by Treatment (Safety Population)
14.1.3.2.2	Summary of Vital Signs – Weight, Respiratory Rate and Temperature by Treatment Sequence (Safety Population)
14.1.4	Summary of Treatment Exposure (Intent-to-Treat Population)
14.1.5	Summary of Medical History (All Randomized Patients)
14.2.1.1.1.1	Summary of Patients Having Positive Plasma Glucose Response by Treatment (Intent-to-Treat Population)
14.2.1.1.1.2	Summary of Patients Having Positive Plasma Glucose Response by Treatment (Modified Intent-to-Treat Population)
14.2.1.1.1.3	Summary of Patients Having Positive Plasma Glucose Response by Treatment (Per-Protocol Population)
14.2.1.1.2.1	Summary of Patients Having Positive Plasma Glucose Response 1 by Treatment (Intent-to-Treat Population)
14.2.1.1.2.2	Summary of Patients Having Positive Plasma Glucose Response 1 by Treatment (Modified Intent-to-Treat Population)
14.2.1.1.2.3	Summary of Patients Having Positive Plasma Glucose Response 1 by Treatment (Per-Protocol Population)
14.2.1.1.3.1	Summary of Patients Having Positive Plasma Glucose Response 2 by Treatment (Intent-to-Treat Population)
14.2.1.1.3.2	Summary of Patients Having Positive Plasma Glucose Response 2 by Treatment (Modified Intent-to-Treat Population)
14.2.1.1.3.3	Summary of Patients Having Positive Plasma Glucose Response 2 by Treatment (Per-Protocol Population)
14.2.1.1.4.1	Summary of Patients Having Positive Symptomatic Response by Treatment (Intent-to-Treat Population)
14.2.1.1.4.2	Summary of Patients Having Positive Symptomatic Response by Treatment (Modified Intent-to-Treat Population)
14.2.1.1.4.3	Summary of Patients Having Positive Symptomatic Response by Treatment (Per-Protocol Population)
14.2.1.1.5.1	Summary of Patients Having Positive Treatment Response by Treatment (Intent-to-Treat Population)

Tables	
Number	Title
14.2.1.1.5.2	Summary of Patients Having Positive Treatment Response by Treatment (Modified Intent-to-Treat Population)
14.2.1.1.5.3	Summary of Patients Having Positive Treatment Response by Treatment (Per-Protocol Population)
14.2.1.2.1	Summary of Plasma Glucose Cmax (mg/dL) by Treatment (Modified Intent-to-Treat Population)
14.2.1.2.2	Summary of Plasma Glucose Tmax (min) by Treatment (Modified Intent-to-Treat Population)
14.2.1.2.3	Summary of Plasma Glucose AUC0-90 (min*mg/dL) by Treatment (Modified Intent-to-Treat Population)
14.2.1.2.4	Summary of Plasma Glucose AUC0-180 (min*mg/dL) by Treatment (Modified Intent-to-Treat Population)
14.2.1.2.5.1	Summary of Time (minutes) to First Positive Plasma Glucose Response After Study Drug Injection by Treatment (Intent-to-Treat Population)
14.2.1.2.5.2	Summary of Time (minutes) to First Positive Plasma Glucose Response After Study Drug Injection by Treatment (Modified Intent-to-Treat Population)
14.2.1.2.5.3	Summary of Time (minutes) to First Positive Plasma Glucose Response After Study Drug Injection by Treatment (Per-Protocol Population)
14.2.1.3.1	Summary of Average Neuroglycopenic Scores, Average Autonomic Scores and Average Total Scores by Treatment and Time Point (Modified Intent-to-Treat Population)
14.2.1.3.2.1	Summary of Time (min) to Symptom Relief (Neuroglycopenic, Autonomic and Total) After Decision to Dose by Treatment (Intent-to-Treat Population)
14.2.1.3.2.2	Summary of Time (min) to Symptom Relief (Neuroglycopenic, Autonomic and Total) After Decision to Dose by Treatment (Modified Intent-to-Treat Population)
14.2.1.3.2.3	Summary of Time (min) to Symptom Relief (Neuroglycopenic, Autonomic and Total) After Decision to Dose by Treatment (Per-Protocol Population)
14.2.1.3.3.1	Summary of Time (min) to Complete Resolution (Neuroglycopenic, Autonomic and Total) After Decision to Dose by Treatment (Intent-to-Treat Population)
14.2.1.3.3.2	Summary of Time (min) to Complete Resolution (Neuroglycopenic, Autonomic and Total) After Decision to Dose by Treatment (Modified Intent-to-Treat Population)
14.2.1.3.3.3	Summary of Time (min) to Complete Resolution (Neuroglycopenic, Autonomic and Total) After Decision to Dose by Treatment (Per-Protocol Population)
14.2.1.3.4.1	Summary of Time (min) to Resolution of the Overall Feeling of Hypoglycemia After Decision to Dose by Treatment (Intent-to-Treat Population)
14.2.1.3.4.2	Summary of Time (min) to Resolution of the Overall Feeling of Hypoglycemia After Decision to Dose by Treatment (Modified Intent-to-Treat Population)

Tables	
Number	Title
14.2.1.3.4.3	Summary of Time (min) to Resolution of the Overall Feeling of Hypoglycemia After Decision to Dose by Treatment (Per-Protocol Population)
14.2.1.3.5.1	Summary of Time (min) to the Minimal Score Post Baseline (Neuroglycopenic, Autonomic and Total) After Decision to Dose by Treatment (Intent-to-Treat Population)
14.2.1.3.5.2	Summary of Time (min) to the Minimal Score Post Baseline (Neuroglycopenic, Autonomic and Total) After Decision to Dose by Treatment (Modified Intent-to-Treat Population)
14.2.1.3.5.3	Summary of Time (min) to the Minimal Score Post Baseline (Neuroglycopenic, Autonomic and Total) After Decision to Dose by Treatment (Per-Protocol Population)
14.2.1.4.1	Summary of Glucagon Preparation Time (min) by Treatment (Intent-to-Treat Population)
14.2.1.4.2	Summary of Glucagon Preparation Time (min) by Treatment (Modified Intent-to-Treat Population)
14.2.1.4.3	Summary of Glucagon Preparation Time (min) by Treatment (Per-Protocol Population)
14.2.1.5	Summary of Study Drug Assignment Questionnaire by Period and by Treatment (Per-Protocol Population)
14.2.2.1.1	Non-inferiority Analysis of Positive Plasma Glucose Response by Treatment (All Enrolled Patients)
14.2.2.1.2	Non-inferiority Analysis of Positive Plasma Glucose Response 1 by Treatment (All Enrolled Patients)
14.2.2.1.3	Non-inferiority Analysis of Positive Plasma Glucose Response 2 by Treatment (All Enrolled Patients)
14.2.2.1.4	Non-inferiority Analysis of Positive Symptomatic Response by Treatment (All Enrolled Patients)
14.2.2.1.5	Non-inferiority Analysis of Positive Treatment Response by Treatment (All Enrolled Patients)
14.2.2.2.1	Non-inferiority Analysis of Plasma Glucose Cmax (mg/dL) by Treatment (Intent-to-Treat Population)
14.2.2.2.2	Non-inferiority Analysis of Plasma Glucose Tmax (min) by Treatment (Intent-to-Treat Population)
14.2.2.2.3	Non-inferiority Analysis of Plasma Glucose AUC0-90 (min*mg/dL) by Treatment (Intent-to-Treat Population)
14.2.2.2.4	Non-inferiority Analysis of Plasma Glucose AUC0-180 (min*mg/dL) by Treatment (Intent-to-Treat Population)
14.2.2.2.5	Non-inferiority Analysis of Time (min) to First Positive Plasma Glucose Response After Study Drug Injection by Population and by Treatment (All Enrolled Patients)
14.2.2.3.1	Non-inferiority Analysis of Time (min) to Symptom Relief (Neuroglycopenic, Autonomic and Total) After Decision to Dose by Population and by Treatment (All Enrolled Patients)
14.2.2.3.2	Non-inferiority Analysis of Time (min) to Complete Resolution (Neuroglycopenic, Autonomic and Total) After Decision to Dose by Population and by Treatment (All Enrolled Patients)

Tables	
Number	Title
14.2.2.3.3	Non-inferiority Analysis of Time (min) to Resolution of the Overall Feeling of Hypoglycemia After Decision to Dose by Population and by Treatment (All Enrolled Patients)
14.2.2.3.4	Non-inferiority Analysis of Time (min) to the Minimal Post Baseline Score After Decision to Dose by Population and by Treatment (All Enrolled Patients)
14.2.2.4	Non-inferiority Analysis of Glucagon Preparation Time (min) by Population and by Treatment (All Enrolled Patients)
14.2.2.5.1	Non-inferiority Analysis of Study Drug Assignment Questionnaire by Treatment (Per-Protocol Population)
14.2.2.5.2	Non-inferiority Analysis of Mean Visual Analog Scale (VAS) (Intent-to-Treat Population)
14.3.1.1	Overview of Adverse Events (Safety Population)
14.3.1.2.1	Summary of Treatment-Emergent Adverse Events by System Organ Class, Preferred Term and by Treatment (Safety Population)
14.3.1.2.2	Summary of Treatment-Emergent Adverse Events by System Organ Class, Preferred Term, Period and by Treatment Sequence (Safety Population)
14.3.1.3.1	Summary of Treatment-Emergent Adverse Events by System Organ Class, Preferred Term, Severity and by Treatment (Safety Population)
14.3.1.3.2	Summary of Treatment-Emergent Adverse Events by System Organ Class, Preferred Term, Severity, Period and by Treatment Sequence (Safety Population)
14.3.1.4.1	Summary of Treatment-Emergent Adverse Events by System Organ Class, Preferred Term, Relationship to Study Drug and by Treatment (Safety Population)
14.3.1.4.2	Summary of Treatment-Emergent Adverse Events by System Organ Class, Preferred Term, Relationship, Period to Study Drug and by Treatment Sequence (Safety Population)
14.3.1.5.1	Summary of Serious Adverse Events Leading to Study Discontinuation by System Organ Class, Preferred Term and by Treatment (Safety Population)
14.3.1.5.2	Summary of Serious Adverse Events Leading to Study Discontinuation by System Organ Class, Preferred Term, Period and by Treatment Sequence (Safety Population)
14.3.1.6.1	Summary of Treatment-Emergent Adverse Events Leading to Study Discontinuation by System Organ Class, Preferred Term and by Treatment (Safety Population)
14.3.1.6.2	Summary of Treatment-Emergent Adverse Events Leading to Study Discontinuation by System Organ Class, Preferred Term, Period and by Treatment Sequence (Safety Population)
14.3.2.1	Listing of Deaths (Safety Population)
14.3.2.2	Listing of Serious Adverse Events (Safety Population)
14.3.2.3	Listing of Treatment-Emergent Adverse Events Leading to Study Discontinuation (Safety Population)
14.3.4.1.1	Summary of Clinical Chemistry Results (Safety Population)
14.3.4.1.2	Summary of Clinical Hematology Results (Safety Population)

Tables	
Number	Title
14.3.4.3	Incidence of Abnormal Laboratory Findings (Safety Population)
14.3.5.1	Summary of Local Tolerability – Subjective Injection Site Discomfort from VAS (Safety Population)
14.3.5.2	Summary of Local Tolerability – Subjective Injection Site Discomfort from Ordinal Pain Scales (Safety Population)
14.3.5.3	Summary of Local Tolerability – Draize Scale (Safety Population)
14.3.6.1.1	Summary of Prior Medications by Treatment (Safety Population)
14.3.6.1.2	Summary of Prior Medications by Treatment Sequence (Safety Population)
14.3.6.2.1	Summary of Concomitant Medications by Treatment (Safety Population)
14.3.6.2.2	Summary of Concomitant Medications by Treatment Sequence (Safety Population)
Listings	
Number	Title
16.1.7	Listing of Randomization (Intent-to-Treat Population)
16.2.1.1	Listing of Patient Disposition (All Patients)
16.2.1.2	Listing of Screen Failure and Inclusion / Exclusion Criteria Assessment (All Patients)
16.2.2.1	Listing of Protocol Deviations (All Patients)
16.2.2.2	Listing of Major Protocol Deviations (All Patients)
16.2.4.1	Listing of Patient Demographic and Baseline Characteristics (Safety Population)
16.2.4.2	Listing of Medical History (Safety Population)
16.2.4.3.1	Listing of Prior Medications (Safety Population)
16.2.4.3.2	Listing of Concomitant Medications (Intent-to-Treat Population)
16.2.5.1	Listing of Study Drug Administration (Intent-to-Treat Population)
16.2.5.2	Listing of Euglycemic Baseline and Hypoglycemia Induction (All Randomized Patients)
16.2.6.1.1	Listing of Dose Monitoring – Plasma Glucose (Intent-to-Treat Population)
16.2.6.1.2	Listing of Dose Monitoring – Pharmacodynamic Parameters (Intent-to-Treat Population)
16.2.6.2.1	Listing of Hypoglycemia Symptom Questionnaire (Intent-to-Treat Population)
16.2.6.2.2	Listing of Average Neuroglycopenic Scores, Average Autonomic Scores and Average Total Scores (Intent-to-Treat Population)
16.2.6.3.1	Listing of Time to Symptom Relief (Intent-to-Treat Population)
16.2.6.3.2	Listing of Time to Complete Resolution (Intent-to-Treat Population)
16.2.6.3.3	Listing of Time to Resolution of the Overall Feeling of Hypoglycemia (Intent-to-Treat Population)
16.2.6.3.4	Listing of Time to the Minimal Post Baseline Score (Intent-to-Treat Population)
16.2.6.4.1	Listing of Positive Plasma Glucose Response (Intent-to-Treat Population)
16.2.6.4.2	Listing of Positive Plasma Glucose Response 1 (Intent-to-Treat Population)
16.2.6.4.3	Listing of Positive Plasma Glucose Response 2 (Intent-to-Treat Population)
16.2.6.4.4	Listing of Positive Symptomatic Response (Intent-to-Treat Population)

Listings	
Title	
16.2.6.4.5	Listing of Positive Treatment Response (Intent-to-Treat Population)
16.2.6.4.6	Listing of Glucagon Preparation Time (Intent-to-Treat Population)
16.2.6.5	Listing of Study Drug Assignment Questionnaire (Intent-to-Treat Population)
16.2.7	Listing of Adverse Events (All Patients)
16.2.8.1	Listing of Laboratory Results: Chemistry (Safety Population)
16.2.8.2	Listing of Laboratory Results: Hematology (Safety Population)
16.2.8.3	Listing of Urine Pregnancy Test Results (Safety Population)
16.2.8.4	Listing of Urine Drug Screen Results (Safety Population)
16.2.9.1	Listing of Injection Site Discomfort – Visual Analog Scale (VAS) (Intent-to-Treat Population)
16.2.9.2	Listing of Injection Site Discomfort – Injection Site Discomfort Description and Duration Questionnaire (Intent-to-Treat Population)
16.2.9.3	Listing of Injection Site Discomfort – Draize Scale (Intent-to-Treat Population)
16.2.10.1	Listing of Vital Signs - Blood Pressure and Heart Rate (Safety Population)
16.2.10.2	Listing of Vital Signs - Height, Weight, Respiratory Rate and Temperature (Safety Population)
16.2.11	Listing of Physical Examinations (Safety Population)
16.2.12	Listing of ECG Findings (Safety Population)
16.2.13	Comments (All Patients)
Figures	
Number	Title
14.2.1.1	Individual Plasma Glucose Concentration by Time and Treatment – Linear Scale (Intent-to-Treat Population)
14.2.1.2	Individual Plasma Glucose Concentration by Time and Treatment – Semi-Log Scale (Intent-to-Treat Population)
14.2.2.1	Mean (+/- SE) Plasma Glucose Concentration by Time and Treatment – Linear Scale (Intent-to-Treat Population)
14.2.2.2	Mean (+/- SE) Plasma Glucose Concentration by Time and Treatment – Semi-Log Scale (Intent-to-Treat Population)
14.2.3.1.1	Individual Average Autonomic Score, Average Neuroglycopenic Score and Average Total Score by Time and Treatment – Linear Scale (Intent-to-Treat Population)
14.2.3.1.2	Individual Average Autonomic Score, Average Neuroglycopenic Score and Average Total Score by Time and Treatment – Semi-Log Scale (Intent-to-Treat Population)
14.2.3.2.1	Mean (+/- SE) Average Autonomic Score, Average Neuroglycopenic Score and Average Total Score by Time and Treatment – Linear Scale (Intent-to-Treat Population)
14.2.3.2.2	Mean (+/- SE) Average Autonomic Score, Average Neuroglycopenic Score and Average Total Score by Time and Treatment – Semi-Log Scale (Intent-to-Treat Population)
14.2.4.1	Individual Subject Plasma Glucose Concentration and Insulin Induction Profile by Time and Treatment (Intent-to-Treat Population)
14.2.4.2	Mean Plasma Glucose Concentration and Hypoglycemia Symptom Score Profiles by Time and Treatment (Intent-to-Treat Population)

Figures	
Number	Title
14.2.5.1.1	Survival Curves of Time (min) to First Positive Plasma Glucose Response After Study Drug Injection by Period and by Treatment (Intent-to-Treat Population)
14.2.5.1.2	Survival Curves of Time (min) to First Positive Plasma Glucose Response After Study Drug Injection by Period and by Treatment (Per-Protocol Population)
14.2.5.2.1	Survival Curves of Time (min) to Symptom Relief (Neuroglycopenic, Autonomic and Total) After Decision to Dose by Period and by Treatment (Intent-to-Treat Population)
14.2.5.2.2	Survival Curves of Time (min) to Symptom Relief (Neuroglycopenic, Autonomic and Total) After Decision to Dose by Period and by Treatment (Per-Protocol Population)
14.2.5.3.1	Survival Curves of Time (min) to Complete Resolution (Neuroglycopenic, Autonomic and Total) After Decision to Dose by Period and by Treatment (Intent-to-Treat Population)
14.2.5.3.2	Survival Curves of Time (min) to Complete Resolution (Neuroglycopenic, Autonomic and Total) After Decision to Dose by Period and by Treatment (Per-Protocol Population)
14.2.5.4.1	Survival Curves of Time (min) to Resolution of the Overall Feeling of Hypoglycemia After Decision to Dose by Period and by Treatment (Intent-to-Treat Population)
14.2.5.4.2	Survival Curves of Time (min) to Resolution of the Overall Feeling of Hypoglycemia After Decision to Dose by Period and by Treatment (Per-Protocol Population)
14.2.5.5.1	Survival Curves of Time (min) to the Minimal Score Post Baseline (Neuroglycopenic, Autonomic and Total) After Decision to Dose by Period and by Treatment (Intent-to-Treat Population)
14.2.5.5.2	Survival Curves of Time (min) to the Minimal Score Post Baseline (Neuroglycopenic, Autonomic and Total) After Decision to Dose by Period and by Treatment (Per-Protocol Population)
14.2.5.6.1	Survival Curves of Glucagon Preparation Time (min) by Period and by Treatment (Intent-to-Treat Population)
14.2.5.6.2	Survival Curves of Glucagon Preparation Time (min) by Period and by Treatment (Per-Protocol Population)

APPENDIX 2: CODE FRAGMENTS

Risk difference test for binary response

```
Proc Freq data = <Data> order=data;  
    weight Count / ZEROS;  
    tables <Treatment>*<Response> / riskdiff;  
    output out = <Out> riskdiff;  
run;
```

Mixed model

```
ods output lsmeans(match_all) = <Out_LSmean>  
           Diffs(match_all) = <Out_Diffs>;  
Proc Mixed data=<Data>;  
    class <Treatment> <Period> <Subject>;  
    model <Value> = <Treatment> <Period> <Treatment>*<Period>;  
    random <Subject> / Type = un;  
    lsmeans <Treatment> / cl DIFF;  
run;
```

Time-to-Event

```
ods output means=<Out_Means> HomTests=<Out_Test>;  
proc lifetest data=<Data>;  
    time <Time>;  
    strata <Treatment>;  
run;
```

Study Drug Assignment

```
proc freq data=<Data>;  
    tables <Treatment>/ BINOMIAL (p=0.50) alpha=0.05;  
    output out=<Out> Binominal;  
    weight count;  
run;
```

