After 180 minutes posttreatment, subjects will resume insulin pump therapy, if applicable, and will be given a meal. Subject may be discharged after 180 minutes posttreatment if their plasma glucose is > 100 mg/dL (5.56 mmol/L) and if medically stable. At the Investigator’s discretion, subjects’ prescribed insulin regimen can be restarted, or the meal can be given sooner, but not earlier than 90 minutes post-glucagon treatment, to prevent hyperglycemia or rebound hypoglycemia.

After a wash-out period of 7 to 28 days, subjects will return to the CRC and the study procedures will be repeated with each subject crossed over to the other treatment. After study-related procedures are performed on each of the treatment days, subjects will be discharged. A Follow-Up Visit will be

XSGP-304 Clinical Protocol
G-Pen (glucagon injection)

	
conducted 2 to 7 days after administration of the final dose of study drug as a safety check.
 
Tolerability will be assessed by comparing AE reports between the G-Pen and GlucaGen Hypokit treatment groups. In addition, at the end of each treatment period the subjects will complete questionnaires to assess injection site discomfort, and the Investigator will use a modified Draize scale to evaluate the injection sites after each administration.

Data management and statistical analysis:	
Data will be entered into an electronic Case Report Form (eCRF) by the study site personnel. Data will be monitored at on-site visits by Xeris personnel or by a contract research organization (CRO) delegated by Xeris. A stand-alone Statistical Analysis Plan (SAP) will be written to detail all protocol specified analyses. The SAP will take precedence over the protocol. The primary endpoint will be analyzed using an exact test procedure based on the conditional distribution for a maximum clinically acceptable non-inferior margin of $\leq 5\%$.

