Sample Size Determination:	
For the primary analysis, a failure is recorded if the subject's plasma glucose fails to reach a concentration >70 mg/dL (>3.88 mmol/L) and fails to increase by at least 20.0 mg/dL (1.11 mmol/L) within 30 minutes of the decision to administer the dose of glucagon. The determination of a constant clinically non-inferior margin for the cure rate difference is generally difficult in practice for a number of reasons. To alleviate this concern, it has been recommended to use an Odds Ratio of success rates for estimation because the corresponding clinically non-inferior margin on the difference scale is getting small when the underlying success rate becomes large and close to 1. In this study, it is expected that the subject's recovery (success rate) will be high and approaching 100%. Since this is a cross-over design and each subject will serve as his/her control, power is improved.
 
The sample size was derived for 80% power of detecting non-inferiority with respect to the Odds Ratio of subject recovery rates at an alpha of 0.025 under a cross-over design. Based on an underlying Odds Ratio of 1.0, and failure rates of 0.2 versus 0.25, 111 subjects are required for the study. With an anticipated 10% drop-out rate, the total sample size for the study is 122 randomized subjects.

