13.2. Sample Size Calculation

For the primary endpoint analysis, a failure is recorded if the subject's plasma glucose fails to reach a concentration >70 mg/dL (>3.88 mmol/L) *and* fails to increase by at least 20.0 mg/dL (1.11 mmol/L) within 30 minutes of the decision to administer the dose of glucagon. The determination of a constant clinically non-inferior margin for the cure rate difference is generally difficult in practice for a number of reasons. To alleviate this concern, it has been recommended to use an Odds Ratio of cure rates because the corresponding clinically non-inferior margin on the difference scale is getting small when the underlying cure rate becomes large and close to 1 [Lui and Chang(a)]. In this study, it is expected that the recovery (cure rate) will be high and approaching 100%. Since this is a cross-over design and each subject will serve as his/her control, power is improved.

The sample size was derived for 80% power of detecting non-inferiority with respect to the Odds Ratio of subject recovery rates at an alpha of 0.025 under a cross-over design [Lui and Chang(b)] Based on an underlying Odds Ratio of 1.0, and rates of 0.20 versus 0.25, 111 subjects are required for the study. With an anticipated 10% drop-out rate, the total sample size for the study is 122 randomized subjects.

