13.3. Primary Endpoint

The primary endpoint comparison will be performed using both the Intention to Treat (ITT) and the per-protocol (PP) populations. The evaluable set for the PP population will be defined as all randomized subjects who, during both study periods, successfully complete the insulin induction procedure, fulfill the criteria for having achieved a hypoglycemic steady state, and successfully receive a dose of both study drugs (G-Pen followed by GlucaGen Hypokit, or GlucaGen Hypokit followed by G-Pen). For analysis of the primary endpoint, a failure for the study treatment (G Pen or GlucaGen Hypokit) will be recorded if the increase in plasma glucose remains < 20 mg/dL (< 1.11 mmol/L) throughout the 0- to 30-minute period from injection of study drug, while a success is defined as an increase in plasma glucose ≥ 20 mg/dL (≥ 1.11 mmol/L) in subjects from a state of insulin-induced hypoglycemia within the 0- to 30-minute period from injection of study drug.

Non-inferiority will be established based on the calculated 95% confidence interval for the difference in failure rates between G-Pen and GlucaGen Hypokit. Non-inferiority will be declared if the upper limit of the 95% confidence interval for the difference in failure rates is $\leq 5\%$; where the absolute failure rate of G-Pen treatment is $\leq 5\%$.

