6 STATISTICAL METHODS

6.1 General Considerations

The statistical analyses will be performed using SAS Version 9.4 (or higher). All tables, figures and listings will be produced in landscape format.

Data will be presented at each scheduled timepoint (nominal time), where applicable. However, time-related endpoints (time to event) will be summarized using actual time.

For actual time, two reference points will be used: (a) decision to dose and/or (b) injection of study drug, which are specified in the primary and secondary endpoint analyses.

The total number of subjects in the study group (N) under the stated population will be displayed in the header of summary tables.

All study data will be included in the study data listings. Listings will be displayed by subject in chronological order, if not stated otherwise.

For tabulated safety summaries, only the scheduled timepoints will be included in the summary tables. Unscheduled assessments will be listed and used for evaluation of worst post-baseline value in categorical assessments, where applicable.

Sample codes and calculations for the efficacy analysis are provided in Appendix 2: Code Fragments. Actual code or procedure usage can differ from these samples, based on the model and conditions that correspond to those pre-specified in the SAP. Additional analysis may be performed for the cases not specified in SAP and will be described in CSR.

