6.5 Analysis of Primary Endpoint

The primary endpoint analysis will be based on the risk difference in rates of failing to achieve Positive Plasma Glucose Response (PGR) of G-Pen versus GlucaGen Hypokit and a 95% CI will be calculated. Non-inferiority will be declared if the upper limit of the 95% confidence interval for the difference in failure rates is $\leq 5\%$; where the absolute failure rate of G-Pen treatment is $\leq 5\%$. This analysis will be repeated for ITT, mITT and PP populations.

Subjects who are missing the primary endpoint for a study treatment will be considered as having a failure in the primary analysis for that treatment administration. This imputation will be conducted for both the ITT and the mITT populations. If a subject received the same two treatment administrations for both periods (Period 1 and Period 2), only the visit with the planned treatment received will be included in the primary analysis and the subject will be considered a failure in the primary analysis for the for unreceived treatment administration (ITT, mITT). For all other analyses, data will be included for only the planned treatment received in those analyses.

A sensitivity analysis will be performed for where all missing data will be considered a success and the same analysis as above completed.

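### The SAP names no confidence interval for the primary non-inferiority limit, and its only sample code (unpaired, Wald by default) can exceed 2.5% error when failures are rare

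*SAP*

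**What the plan says.** SAP 6.5 sets the decision rule: "Non-inferiority will be declared if the upper limit of the 95% confidence interval for the difference in failure rates is" at most 5%, with an observed G-Pen failure rate of at most 5%. Neither 6.5 nor SAP 5.3.6.1 names the interval or says how the pairing is handled. The only specification is the Appendix 2 fragment, "tables <Treatment>*<Response> / riskdiff", and SAP 6.1 makes even that non-binding: "Actual code or procedure usage can differ from these samples".

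The protocol does not settle the matter. Its synopsis says "The primary endpoint will be analyzed using an exact test procedure based on the conditional distribution", while section 13.3 says "Non-inferiority will be established based on the calculated 95% confidence interval for the difference in failure rates", again with no type given. The SAP supersedes the protocol and undertakes to identify substantial differences, but its Section 10 lists only the change for timing parameters. The exact test is neither carried over nor recorded as dropped.

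For missing outcomes counted as failures, SAP 6.5 says: "This imputation will be conducted for both the ITT and the mITT populations". PP is not covered.

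The documents give two pictures of the failure rate. The synopsis sample-size text uses "failure rates of 0.2 versus 0.25, 111 subjects are required for the study"; Protocol 13.2 and SAP 4.2 repeat the figures simply as rates. The same sections expect success close to 100%.

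**The concern.** With an unnamed interval, two analysts following the same SAP can reach opposite primary conclusions from the same data. If the sample code is run as printed, the limit is an unpaired Wald limit, which is too narrow when failures are few. At zero failures in both arms it has no width at all.

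Rare failures are the only setting in which this trial can succeed, because the G-Pen cap rules out the 20 to 25% range. What is at stake is a false non-inferiority claim, or a result that turns on a software default when only two or three failures occur.

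**Working it through.** **Inputs.** Margin and cap, both 5% (SAP 6.5). One-sided 2.5%, from alpha 0.025 (SAP 4.2). n=111 evaluable in both periods and n=122 randomized (Protocol synopsis, SAP 4.2). Reference failure of 0 to 3% is my reading of success close to 100%. Within-subject concordance is not given, so three cases are run: independence, every reference failure shared with G-Pen (full), and midway (halfway). That plain RISKDIFF gives Wald limits is knowledge of the software, not of the documents.

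**The plan's own figures.** There is no stated error rate to reproduce. The 111 cannot be rebuilt, because no odds-ratio margin or discordance is given; 111 × 1.1 = 122.1 matches the 122. Both sizes are taken as given.

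**Planning rates.** If true G-Pen failure were 20%, the chance of meeting the cap would be P(X ≤ 5 of 111) ≈ 2.7 in a million, or P(X ≤ 6 of 122) ≈ 2 in a million. Wald error at 0.25 versus 0.20, ignoring the cap, is 2.6%. So Wald is sound there, but the trial could not succeed.

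**Limits at 2 versus 0.**

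Wald: d + 1.96·√(p₁q₁/n + p₂q₂/n).
- n=111: 0.01802 + 1.96·√(0.01802 × 0.98198/111) = 0.0428.
- n=122: 0.01639 + 1.96·√(0.01639 × 0.98361/122) = 0.0389.

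Tango: solve (b − c − nΔ)/√(n[2q̃ + Δ(1 − Δ)]) = −1.96, where b and c count subjects failing on G-Pen only and on GlucaGen only, and q̃ is the constrained estimate of the GlucaGen-only probability. Here c=0 and q̃=0, so it reduces to the Wilson limit, (x + z²/2 + z√(x(n−x)/n + z²/4))/(n + z²).
- n=111: (3.921 + 1.96·√2.924)/114.84 = 0.0633.
- n=122: (3.921 + 1.96·√2.927)/125.84 = 0.0578.

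| Interval, 2 vs 0 | n=111 | n=122 |
|---|---|---|
| Wald | 4.28% | 3.89% |
| Continuity-corrected Wald | 5.18% | 4.71% |
| Agresti-Caffo | 5.20% | 4.74% |
| Bonett-Price | 5.22% | 4.76% |
| Tango | 6.33% | 5.78% |
| Newcombe | 6.33% | 5.78% |
| Miettinen-Nurminen | 6.35% | 5.79% |

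At 3 versus 2, Wald declares (4.80% and 4.37%). With 0, 1 or 2 subjects failing on both drugs, Tango gives 6.11, 5.55 or 4.93% (n=111) and 5.58, 5.07 or 4.50% (n=122). At 0 vs 0, 1 vs 0 and 3 vs 0 the two methods agree.

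**Error at a true 5-point difference.** With reference failure 0, Wald declares at up to 2 G-Pen failures (3 vs 0 gives 5.72% and 5.21%), so the error is P(X ≤ 2 | n, 0.05) = 8.0% (n=111) or 5.3% (n=122). Tango declares at up to 1 failure: 2.3% or 1.4%. The other cells come from multinomial enumeration with the cap applied.

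| Wald error by reference failure | 0% | 0.5% | 1% | 2% | 3% |
|---|---|---|---|---|---|
| Independent, n=111 | 8.0 | 6.2 | 5.5 | 4.7 | 3.8 |
| Independent, n=122 | 5.3 | 6.1 | 5.3 | 4.1 | 3.6 |
| Halfway, n=111 | | | 4.7 | 3.4 | 2.4 |
| Halfway, n=122 | | | 4.6 | 3.0 | 2.1 |
| Full, n=111 | | | 3.9 | 2.0 | 1.1 |
| Full, n=122 | | | 3.8 | 1.9 | 0.9 |

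Tango over 0 to 3% in all three cases: 1.2 to 2.3%.

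**Pairing alone is not the cure.** Paired Wald at 1% reference failure with full concordance gives 7.8% (n=111) and 5.3% (n=122). The Wald approximation is the cause.

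**The case against.** The strongest objection concerns imputation. The 122 allows for 10% dropout, and ITT counts a missing outcome as a failure. Suppose 122 − 111 = 11 subjects each miss one dose, split 5 and 6 between drugs, with independent outcomes. Wald error is then 0.0 to 0.5% for reference failure of 0 to 2%, and 6 versus 6 imputed failures gives a Wald limit of 5.43%, which does not declare. This stands: at planned dropout the inflation is a PP matter, and in ITT or mITT it needs almost complete data. But SAP 6.5 repeats the analysis in all three populations without naming the deciding one, and PP has no such buffer.

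Other points carry part of their weight:
- The code is only a sample. True, but that leaves the deciding interval open, which is the defect.
- At n=122 three other intervals also declare at 2 versus 0, so the split is not peculiar to Wald. True, and it shows how much rests on the choice.
- Tango runs below nominal and costs power. True; the cost is given with the fix.
- Protocol 13.3 already uses a confidence interval, so the conflict with the exact test starts inside the protocol. True; the synopsis needs aligning as well. The exact test was not evaluated here.
- With high concordance Wald is conservative from about 2% reference failure. True, but the documents give no concordance on which to rely.

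**Conclusion.** The concern holds and should be fixed. The plan leaves the interval behind its primary claim unspecified, and its one illustration can run at about one and a half to three times the nominal error (3.6 to 8.0% against 2.5%) when periods are independent and reference failure is 0 to 3%. The 8.0% is the extreme: no reference failures at all, at n=111.

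The inflation shrinks with concordance and is gone by 3% reference failure in the halfway case. It is also gone if imputed failures lift the reference rate to 4.5 or 5% (2.4 and 1.9% at n=122, independent). The size therefore rests on two things the documents do not give, the concordance and the exact failure rate. The missing specification itself rests on neither.

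**What to change.** In SAP 6.5, name one interval: the Tango score 95% confidence interval for the paired risk difference. Keep the 5% margin and the 5% cap. In Appendix 2, replace the fragment with a per-subject cross-tabulation of G-Pen outcome by GlucaGen outcome that computes this interval. Record the departure from the synopsis's exact test in SAP Section 10 and align the synopsis with Protocol 13.3. Protocol 13.1 calls for an amendment where a change to the primary analysis is major.

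For the binary secondary endpoints (SAP 6.6.1), use the same interval only for subjects evaluable in both periods. SAP 5.3.6.2.3 sets a baseline-score condition for symptom relief; if it also governs the binary symptomatic response, some subjects will be evaluable in one period only, and the SAP should say how they are handled.

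The cost is wording, a short piece of code and possibly an amendment, with no new data. Power at equal failure in both arms, Tango versus Wald, independent periods:

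| Failure rate | n=111 | n=122 |
|---|---|---|
| 0.5% | 90 vs 98% | 89 vs 99% |
| 1% | 76 vs 92% | 74 vs 94% |
| 2% | 57 vs 77% | 59 vs 79% |

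The largest loss found over 0.25 to 3% is 22 points (n=122, 1.5%: 65 vs 87%). Under independence Tango falls below the planned 80% from 1% failure up, and the sponsor should know this before adopting it. At halfway concordance the loss is smaller (n=111: 90 vs 95% at 1%, 76 vs 82% at 2%). At full concordance nothing is lost (at 2%: 97.5 vs 92.7% for n=111, 98.8 vs 96.3% for n=122). Part of Wald's advantage is simply its inflated error.
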